STATISTICAL ANALYSIS (as applicable to active substudies)

Key analysis populations

Safety / Intent-to-treat population: All patients with an eligible FGFR1–3 GA who received at least one dose of derazantinib or atezolizumab. Safety data will be summarized according to the treatment actually received.

Modified intent-to-treat (mITT) population: All patients who received at least one dose of derazantinib or atezolizumab, and have at least one post-baseline imaging assessment in accordance with RECIST 1.1, or documented clinical progression (every effort should be made to objectively assess radiographic progression). The mITT population will be used for all primary efficacy endpoint analyses.

Analysis of the primary efficacy endpoint

The primary efficacy endpoint will be ORR, defined as the achievement of confirmed CR or PR using RECIST 1.1, as assessed by BICR. Point estimates and 2-sided 95% confidence intervals (CIs) will be provided. The primary analysis will be performed on the mITT population and repeated on the per-protocol population.

Analysis of the primary safety endpoint (Substudies 3 and 5)

Safety interim analyses will be performed once up to 10 patients have been enrolled and full safety data are available in Substudies 3 and 5 to determine if the revised dosing regimen of derazantinib 200 mg BID either as monotherapy or in combination with atezolizumab is safe and tolerable. The safety evaluation will comprise updating a three-parameter cumulative Bayesian linear regression model (BLRM) with overdose control (EWOC) design with monotherapy and combination therapy for the incidence of DLTs to strictly manage the risk of excessive toxicity (see Section 8.3.5.1). The prior data will comprise the current number of DLTs observed at each derazantinib dose previously explored. With an acceptable target toxicity range for a dose defined as a probability of toxicity of 10% to 25% and an overdosing range of $\geq 25\%$, the posterior probability of overdosing will be updated over time. Data resulting in a posterior probability of overdosing for a dose in excess of 25% will be determined as unacceptable. This ensures a tolerable dose is chosen for subsequent evaluation of efficacy.

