4.5.3 Replacement of patients

Patients who are non-evaluable for efficacy (see Section 8.2.2) are to be replaced.

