13. Tumor assessments performed as SoC prior to obtaining informed consent and within 28 days of the first dose of study treatment on C1D1 may be used rather than repeating tests. The first on-study tumor imaging assessments will be performed after 9 weeks on study, and will be repeated every 9 weeks (± 7) from C1D1 (i.e., at C4D1, C7D1, C10D1) and every 12 weeks (± 7) from C10D1 (i.e., at C14D1, C18D1, etc.) thereafter (with additional scans as clinically indicated and as per RECIST 1.1 criteria) until disease progression, death, or loss of follow-up. A tumor assessment should be performed at the End-of-Treatment visit only if the prior scan was not done within 4 weeks (28 days) prior to this visit, or if the prior scan did not show radiographic disease progression (see Sections 5.2.2.7 and 5.3.3.2). The same radiographic procedure as used at the SV must be used throughout the study for each patient to follow target lesions, and results must be reviewed by the Investigator before dosing at the next cycle. Imaging timing should be based on the first dose at C1D1, should follow calendar days, and should not be adjusted for delays in cycle starts.
14. For pre-dose PK blood sampling at C1D15 (**all substudies**), and C1D8, C2D8 and C2D15 (**safety interim analysis patients in Substudies 3 and 5**), administer derazantinib at the study site.
15. Derazantinib PK blood (plasma) sampling will be performed according to the following schedule:
 - a. **Rich PK profiling - Applicable to safety interim analysis patients in Substudy 3 and 5 only:**
 - C1D1, prior to derazantinib dose, and 1 hour (± 5 minutes), 2 hours (± 5 minutes), 4 hours (± 15 minutes), 8 hours (± 30 minutes), 10 hours (± 30 minutes), 12 hours (± 30 minutes; prior to the second dose administration), 24 hours after first derazantinib administration (i.e., 12 hours post second dose administration but within 1 hour prior to the third dose).
 - C1D8, pre-dose (within 1 hour prior to the next dose), and 6–8 hours after derazantinib administration.
 - C1D15, pre-dose (within 1 hour prior to the next dose), and 6–8 hours after derazantinib administration.

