8.2.2 Modified intent-to-treat population

For all efficacy endpoint analyses, a mITT population will be used, comprising all patients who received at least one dose of derazantinib or atezolizumab, and have at least one post-baseline imaging assessment in accordance with RECIST 1.1, or documented clinical

progression (every effort should be made to objectively assess radiographic progression). Non-evaluable patients will be replaced.

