8.3.4.1 Primary endpoint

The primary endpoint in all substudies will be ORR, defined as the achievement of confirmed CR or PR using RECIST 1.1, as assessed by BICR. Point estimates and 2-sided 95% CIs will be provided. The primary analysis will be performed on the mITT population and repeated on the PP population.

Interim analyses for stage transition in the efficacy-estimating substudies will be performed when the number of patients specified below have been enrolled, have received at least one dose of study drug, and have at least had one post-baseline tumor imaging assessment, but no later than after the completion of Cycle 9 (i.e., have received approximately 27 weeks of treatment and had up to four post-baseline study imaging assessments). If the required number of responses per BICR specified for each cohort has not been observed at the time of enrollment of the last patient to Stage 1, enrollment may be suspended, or the cohort may be terminated due to apparent futility.

If the required number of responses per BICR specified for each cohort is reached earlier, interim analyses may be performed earlier.

The final analysis for ORR will be performed once all patients have been enrolled per cohort/substudy and have been followed for approximately up to 27 weeks of treatment (i.e., each patient had up to four post-baseline study imaging assessments). Patients without efficacy assessments are considered non-responders, and included in the analysis. Hypothesis testing (null hypothesis [H_0] versus alternative hypothesis [H_A]) will be performed at the interim and final analyses as per the below specified decision rules:

- **Substudy 1**

H_0 : $p \leq 0.21$ versus H_A : $p > 0.21$.

If there are five or fewer patients with a response (defined as a CR or PR) in the first 35 evaluable patients included in the interim analysis, the substudy will be stopped. If not, an additional 39 patients will be enrolled, for a total of 74 evaluable patients. The null hypothesis will be rejected if 22 or more responses are observed in these 74 patients.

- **Substudy 3**

$H_0: p \leq 0.25$ versus $H_A: p > 0.45$.

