8.3.10 Handling of missing data and discontinuations

Missing data will not be imputed. Patients whose clinical response is unknown or not reported will be treated as non-responders.

Reasons for discontinuation and the date of discontinuation from the study will be listed, and dates of first and last study drug provided as well as the duration of exposure to study drug and date. Summary tables will be provided by substudy and cohort.

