For patients with PR or CR, the Investigator should make every attempt to perform the confirmation scan 4 to 5 weeks after the last scan was performed. Radiographic disease progression must be confirmed by central radiology prior to treatment discontinuation if progression is seen on first or second post-treatment scan.

Patients with a global deterioration of health status requiring discontinuation of treatment without objective evidence of disease progression at that time should be reported as 'symptomatic deterioration'. Every effort should be made to document objective progression even after discontinuation of treatment. Symptomatic deterioration is not a descriptor of an objective response: it is a reason for stopping study therapy. The objective response status of such patients is to be determined by evaluation of target and non-target disease.

For equivocal findings of progression (e.g., very small and uncertain new lesions; cystic changes or necrosis in existing lesions), treatment may continue until the next scheduled assessment. If at the next scheduled assessment, progression is confirmed, the date of progression should be the earlier date when progression was suspected.

Frequency of tumor re-evaluation

In this study, tumor measurement will be conducted at baseline, and once every 9 weeks (every three cycles) for the first 27 weeks, and every 12 weeks (every four cycles) thereafter while the patient is on treatment or as clinically indicated until progression of disease, withdrawal of consent, or death. Tumor measurement will also be performed during the End of Treatment visit if it is not done within 28 days of the End of Treatment visit date or if prior scan did not show radiographic disease progression.

Baseline tumor assessments must be performed within 4 weeks (28 days) of the first dose of treatment.

All efforts must be made to ensure consistency between the baseline measurements and all subsequent measurements in reference to utilization of scanning methods, equipment, technique (including slice thickness and field of view), and the radiographic interpreter.

The radiological evaluation must include CT or MRI scanning of the chest, abdomen, and pelvis. Any additional suspected sites of disease should also be imaged. All evaluations must meet the SoC for imaging of lesions in the respective organ(s).

All target and non-target sites are evaluated at each time point of tumor assessment.

Confirmatory measurement/duration of response

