5.1. Safety Population/ Intent-to-treat Population

The safety/intent-to-treat (ITT) population consists of all patients with an eligible FGFR1–3 GA who received at least one dose of derazantinib or atezolizumab. Safety data will be summarized according to the treatment actually received.

In the primary safety comparison, patients who crossover to derazantinib-atezolizumab combination are censored at time of crossover (i.e., AEs occurring during treatment with derazantinib-atezolizumab combination are excluded for Cohort 4a patients).

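### Protocol and SAP define the primary ORR set differently for a death before the first scan, the SAP does not declare the change, and no planned ORR includes the dosed patients who are replaced

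*Protocol*

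**What the plan says.** The protocol synopsis states that "The mITT population will be used for all primary efficacy endpoint analyses". Protocol 8.2.2 admits a dosed patient to mITT by either of two routes: the patient must "have at least one post-baseline imaging assessment in accordance with RECIST 1.1", or have documented clinical progression. Death is not a route. SAP 5.2 repeats the definition and adds death as a third route. Both sections replace non-evaluable patients, and Protocol 4.5.3 ties evaluability to the mITT section: "Patients who are non-evaluable for efficacy (see Section 8.2.2) are to be replaced".

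For patients in the analysis, Protocol 8.3.4.1 and SAP 6.3.1.1 say that "Patients without efficacy assessments are considered non-responders, and included in the analysis". Protocol 8.3.10 and SAP 6.1.4 add a general rule: "Patients whose clinical response is unknown or not reported will be treated as non-responders".

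Protocol 8.3.4.1 and SAP 6.3 repeat the ORR analysis in the per-protocol set only. Protocol 8.2.3 and SAP 5.3 define that set as mITT patients without relevant major deviations. The Safety/ITT set is defined in both documents, but neither assigns an ORR to it. SAP 6.8, the section for changes from the protocol, lists only the dropped IPCW model.

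On timing, "The first on-study tumor imaging assessments will be performed after 9 weeks on study" (Protocol Table 1, footnote 13).

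**The concern.** With the first scan at week 9, a patient can die before any post-baseline image exists. If no clinical progression was documented, the two documents treat that patient in opposite ways: the protocol removes and replaces, the SAP retains as a non-responder. This affects conduct as well as reporting. The interim rules count the first 35, 18, 16 or 13 evaluable patients (Substudies 1, 3, 4 per cohort, and 5), so the definition decides who forms Stage 1 and when it is full.

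The second matter concerns what a reader of the results can see. A confirmed response needs two assessments at least four weeks apart (SAP 6.3.1.1), so an unscanned patient cannot be a responder. Removing such patients and enrolling others in their place can leave ORR unchanged or raise it, but never lower it, relative to all dosed patients. A repeat analysis in a subset of mITT cannot show this.

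**Working it through.** **1. The definitions side by side.** For a dosed patient with no post-baseline scan:

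| Patient | Protocol 8.2.2 and 4.5.3 | SAP 5.2 |
|---|---|---|
| Documented clinical progression | In, non-responder | In, non-responder |
| Died, no documented clinical progression | Out, replaced | In, non-responder |
| Alive, no documented clinical progression | Out, replaced | Out, replaced |

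The conflict is confined to the second row. The third row is excluded under both documents.

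**2. The plan's own figures.** Inputs are the cut-offs in Protocol 8.1 and SAP 6.1.6. Exact two-stage binomial enumeration gives type I error / power of 0.0463 / 0.8001 (Substudy 1), 0.0462 / 0.8098 (Substudy 3), 0.0448 / 0.8027 (Substudy 4, per cohort) and 0.0387 / 0.8189 (Substudy 5). All agree with the stated values, so the designs are correct for evaluable patients. For Substudy 1 the Stage 1 cut-off is seven, as in Protocol 8.1.1 and the SAP. Protocol 8.3.4.1 prints five, which is a separate inconsistency; five gives a type I error of 0.0484, not 0.0463.

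**3. One early unscanned death in Stage 1.** Let n1 be the Stage 1 size, r1 the largest count that stops the cohort, and p1 the design response rate, taken as the rate in the other patients. Under the protocol the patient is replaced, so the chance of stopping is P(X ≤ r1) with X binomial(n1, p1). Under the SAP one of the n1 places is a certain non-response, so X is binomial(n1 − 1, p1).

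| Substudy | n1 | r1 | p1 | Protocol | SAP | Difference (points) |
|---|---|---|---|---|---|---|
| 1 | 35 | 7 | 0.34 | 0.0539 | 0.0668 | 1.3 |
| 3 | 18 | 4 | 0.45 | 0.0411 | 0.0596 | 1.9 |
| 4, per cohort | 16 | 1 | 0.20 | 0.1407 | 0.1671 | 2.6 |
| 5 | 13 | 1 | 0.30 | 0.0637 | 0.0850 | 2.1 |

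**4. ORR in all dosed patients.** The documents give no replaced share; 5% of dosed patients is an assumption. The expected number replaced is n/0.95 − n = 3.9, 1.9, 2.6 and 1.4, rounded to 4, 2, 3 and 1. For a result exactly at the final cut-off, with Clopper-Pearson 95% intervals:

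| Substudy | mITT | All dosed |
|---|---|---|
| 1 | 22/74 = 29.7% (19.7 to 41.5) | 22/78 = 28.2% (18.6 to 39.5) |
| 3 | 14/36 = 38.9% (23.1 to 56.5) | 14/38 = 36.8% (21.8 to 54.0) |
| 4, per cohort | 7/50 = 14.0% (5.8 to 26.7) | 7/53 = 13.2% (5.5 to 25.3) |
| 5 | 6/26 = 23.1% (9.0 to 43.6) | 6/27 = 22.2% (8.6 to 42.3) |

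The smallest shift is 14.00 − 13.21 = 0.79 points (Substudy 4) and the largest 38.89 − 36.84 = 2.05 points (Substudy 3).

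**The case against.** An evaluable primary set with pre-specified replacement is a declared design choice in an open-label Phase 1b/2 study. That stands, and the point does not ask for mITT to be dropped.

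The death conflict is narrow. Protocol 7.4.3.1.1 has progression recorded as an adverse event when its outcome is death; if that record counts as documented clinical progression, both texts keep the patient. The SAP version is also the more conservative, and Protocol 8 leaves analysis detail to the SAP. This limits the size of the problem but does not say which definition governs replacement during enrolment.

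Few patients should be affected. An end-of-treatment scan is due if none was done within 28 days "or if prior scan did not show radiographic disease progression" (Protocol Appendix 2). SAP 6.2.1 tabulates dosed and mITT numbers, lists exclusions and reports reasons for discontinuation, so a reader could work out an all-dosed ORR. That stands as to size. A derivable figure is still not a pre-specified estimate, and no scan can be obtained after a death.

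The interim effect is conditional on such a death, and no probability for one is given. All Stage 1 data inform the decision (Protocol 8.1). Substudy 1 interim results were already known at protocol version 5.0, so its row may no longer be prospective.

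A reader might infer that the non-responder sentence contradicts the exclusion of unscanned patients. The documents do not support that. Protocol 8.2.2 and 8.3.4.1 and SAP 6.3 fix mITT as the efficacy set, and within it the sentence applies to unscanned patients who enter through clinical progression or, in the SAP, death.

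**Conclusion.** The point holds and should be fixed, though its numerical effect is modest. The primary set differs between the documents for one defined kind of patient, the difference is undeclared, and it carries through to replacement and Stage 1 counting. Given one such death, the futility-stop probability at p1 changes by 1.3 to 2.6 percentage points, assuming p1 is the rate in the other patients and, for Substudy 1, that the interim is still ahead.

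Separately, no planned ORR includes the replaced patients. The direction of that effect is certain. Its size, about 0.8 to 2 points at an assumed 5% replaced, is small beside intervals about 20 to 35 points wide.

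A reader might go further and infer that the stated type I errors are too low. That would require the null rates to be rates in all treated patients, which the documents do not say. For evaluable patients, on whom the designs are sized, the stated errors are exact.

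**What to change.** Keep mITT as the primary set and leave every cut-off unchanged.

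- Use one definition of mITT and evaluable in protocol and SAP, covering the analysis, replacement and the interim counts. Settle whether a death before the first scan counts as evaluable, and list the change in SAP 6.8.
- Pre-specify a supplementary ORR with exact 95% CI in all patients who received at least one dose, counting anyone without a confirmed CR or PR as a non-responder. The Safety/ITT set also requires an eligible FGFR1–3 aberration and mITT does not, so either use all dosed patients or state that difference.
- Report the number replaced per cohort beside it.
- Optionally, write into the non-responder sentence that it applies within mITT.

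The cost is a wording change in both documents and one extra table per substudy. The supplementary ORR may be slightly below the primary one. Adding the supplementary table costs no power, because the primary set and decision rules stay in place.

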8.1 Sample size considerations by substudy

Simon's two-stage designs ([Simon 1989](#)) will be used for **Substudies 1 and 4**, and Fleming's two-stage designs ([Fleming 1982](#)) will be used for **Substudies 3 and 5**. At the time point of interim analysis and decision to transition from Stage 1 to 2, all data collected in Stage 1 patients will be used to inform the decision. Should the required number of events (i.e., responses) be reached prior to full enrollment to Stage 1, the time point for decision to transition from Stage 1 to Stage 2 may be taken before the stage is fully enrolled. If the required number of events (i.e., responses) is not reached at the time of full enrollment to Stage 1, further enrollment may be suspended to allow for all patients to be exposed to derazantinib or derazantinib-atezolizumab in combination for at least 3 months or until disease progression.

The use of such designs will limit the number of overall exposed patients to a maximum of approximately 98, should either derazantinib or derazantinib-atezolizumab in combination be ineffective in Stage 1 of all efficacy-estimating substudies, as compared to a maximum of 246 patients if derazantinib or derazantinib-atezolizumab are considered to be effective in all cohorts.

Assuming an overall incidence of approximately 20% qualifying *FGFR1-3* GAs ([Helsten 2016](#)), up to approximately 680 patients will be screened for *FGFR1-3* GAs, depending on the extent of preexisting molecular testing. Assuming that pre-treatment with an FGFR inhibitor was based on a known *FGFR* GA status, no repeated testing is anticipated for the approximately 100 patients enrolled in Substudy 4.

8.1.1 Substudy 1

The null hypothesis that the true ORR is $p_0 \leq 0.21$ will be tested against a one-sided alternative. In Stage 1, 35 evaluable patients will be enrolled. If 7 or fewer patients with an objective response are observed in Stage 1, the cohort will be stopped. If 8 or more patients with an objective response (defined as a CR or PR) are observed in these 35 patients, an additional 39 patients will be enrolled, for a total of 74 patients. The null hypothesis will be rejected if 22 or more responses are observed in these 74 patients. The one-sided Type I error rate is 0.0463, and the power is 0.8001 when the true ORR is $p_1 = 0.34$ and higher than the ORR of 32.2%, the highest reported value for an FGFR inhibiting treatment in mUC patients ([Balversa USPI](#)).

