The ORR of 21% for the null hypothesis reflects the lower range of ORR seen in recent clinical studies of UC patients with FGFR GAs (Loriot 2019, Necchi 2018, Pal 2018).

8.1.2 Substudy 3

The Fleming’s two-stage design sample size calculation is based on the assumption that first-line cisplatin-ineligible patients with advanced or metastatic mUC expressing *FGFR1–3* GAs treated with 200 mg BID derazantinib in combination with 1200 mg atezolizumab Q3W will attain a clinically meaningful ORR of approximately 45%, which is similar to that obtained with erdafitinib and cetrelimab (Moreno 2020), or rogaratinib and atezolizumab (Rosenberg 2020), in combination for this patient population, and is considered the benchmark by oncology experts. An ORR of 25% (estimated mean ORR with immune checkpoint-inhibiting monotherapy available for cisplatin-ineligible patients) is not considered sufficiently effective to warrant further clinical investigation.

Using a Fleming’s two-stage design, a total sample size of 36 is required to test a null hypothesis of $H_0: \pi \leq 0.25$ versus an alternative hypothesis of $H_a: \pi \geq 0.45$ with a one-sided target significance level of 0.05 and target power of 80%, where π is the true proportion of successes. This design results in an exact type 1 error rate of 0.046, an exact level of power of 81%, and an average sample size of 27 patients under H_0 and 31 under H_a . Table 7 summarizes the required samples sizes and required responses to either accept or reject H_0 .

Table 7 Summary of sample size and required responses of proposed two-stage Fleming design

	Sample size		Responders to accept H_0		Responders to reject H_0	
	N	n	%	n	%	
Stage 1	18	4	22.2	10	55.6	
Stage 2	36	13	36.1	14	38.9	

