 * If a CR is truly met at first time point, then any disease seen at a subsequent time point, even disease meeting PR criteria relative to baseline, makes the disease PD at that point (since disease must have reappeared after CR). Best response would depend on whether minimum duration for SD was met. However, sometimes 'CR' may be claimed when subsequent scans suggest small lesions were likely still present and in fact the patient had PR, not CR at the first time point. Under these circumstances, the original CR should be changed to PR and the best response is PR.

As specified in RECIST 1.1, repeated 'NE' time point assessments complicate best response determination. Should a CR/PR be followed by a NE response and then a CR/PR, then confirmed response would be achieved (as an example PR-NE-PR will be considered as a confirmed response).

Note that iRECIST criteria (an adaptation of RECIST 1.1 to account for the tumor response patterns seen with immunotherapeutic drugs ([Seymour 2017](#))) will also be considered in exploratory analyses.

Patients without efficacy assessments are considered non-responders, and included in the analysis.

Hypothesis testing (null hypothesis [H₀] versus alternative hypothesis [H_A]) will be performed at the interim and final analyses as specified below:

Substudy 1

H₀: p ≤ 0.21 versus H_A: p ≥ 0.34

If there are seven or fewer patients with an objective response (defined as a confirmed CR or PR) in the first 35 evaluable patients included in the interim analysis, the substudy will be stopped. If not, an additional 39 patients will be enrolled, for a total of 74 evaluable patients. The null hypothesis will be rejected if 22 or more objective responses are observed in these 74 patients.

Substudy 3

H₀: p ≤ 0.25 versus H_A: p ≥ 0.45

If there are four or fewer patients with an objective response (defined as a confirmed CR or PR) in the first 18 evaluable patients included in the interim analysis, the cohort will be stopped. If not, an additional 18 patients will be enrolled, for a total of 36 evaluable patients. The null hypothesis will be rejected if 14 or more objective responses are observed in these 36 patients (or if 10 or more responses are observed in

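### Substudy 1's Stage 1 futility boundary is 5 of 35 in Protocol 8.3.4.1 but 7 of 35 in Protocol 8.1.1 and the SAP, so 6 or 7 responses lead to opposite decisions

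*Protocol*

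**What the plan says.** Substudy 1 is a Simon two-stage design with 35 evaluable patients in Stage 1, 39 more in Stage 2 (74 in total), and rejection of the null at 22 or more responses. These numbers agree wherever they appear. The Stage 1 stopping boundary does not.

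- **Protocol 8.1.1 (sample size):** "If 7 or fewer patients with an objective response are observed in Stage 1, the cohort will be stopped". The cohort continues at 8 or more. The same paragraph gives the operating characteristics: "The one-sided Type I error rate is 0.0463, and the power is 0.8001", with power evaluated at a true ORR of 0.34.
- **Protocol 8.3.4.1 (primary endpoint analysis):** the Substudy 1 bullet stops on "If there are five or fewer patients with a response (defined as a CR or PR) in the first 35 evaluable patients" and otherwise enrols the further 39, so it continues at 6 or more. The section presents these bullets as the decision rules for the interim and final hypothesis tests.
- **SAP 6.3.1.1:** "If there are seven or fewer patients with an objective response (defined as a confirmed CR or PR) in the first 35 evaluable patients". SAP 3.1 and 6.1.6.1 also say 7 or fewer.

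SAP 6.8, which lists changes from the protocol's methods, mentions only the dropped inverse-probability-of-censoring analysis.

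**The concern.** Both boundaries stand in current protocol text, and both are worded as binding. At 6 or 7 responses in 35 they cannot both be obeyed: one section continues to 74 patients and the other stops at 35. This is the go/no-go rule for the primary endpoint in the largest single cohort of the study.

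The choice also affects patient exposure. Protocol sections 1.5.1 and 1.5.4 rely on the two-stage designs to limit the number of patients given a futile treatment. A lower futility boundary weakens that protection, so it matters which number is the real design.

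**Working it through.** **Inputs.** All come from Protocol 8.1.1 unless noted.

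- Null ORR p0 = 0.21 ("The ORR of 21% for the null hypothesis reflects the lower range of ORR"); alternative ORR p1 = 0.34.
- One-sided test: the null "will be tested against a one-sided alternative".
- n1 = 35, n2 = 39, n = 74; reject at 22 or more responses.
- Stage 1 boundary r1 (stop if responses ≤ r1): 7 in 8.1.1 and the SAP, 5 in 8.3.4.1.

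**Formulas.** X1 is the number of Stage 1 responses and X2 the number of Stage 2 responses.

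- P(reject | p) = Σ over x1 = r1+1 to 35 of P(X1 = x1) × P(X2 ≥ 22 − x1), with X1 ~ Bin(35, p) and X2 ~ Bin(39, p).
- Probability of early stopping: PET = P(X1 ≤ r1).
- Expected N = 35 + 39 × (1 − PET).

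**Reproducing the stated figures.** With r1 = 7, the sum is 0.04631 at p = 0.21 and 0.80015 at p = 0.34. These are the protocol's 0.0463 and 0.8001. The neighbouring boundaries do not match:

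| r1 | Type I error (p = 0.21) | Power (p = 0.34) | PET at p = 0.21 | Expected N at p = 0.21 |
|---|---|---|---|---|
| 5 | 0.0484 | 0.8138 | 0.227 | 65.2 |
| 6 | 0.0479 | 0.8105 | 0.376 | 59.3 |
| 7 | 0.0463 | 0.8001 | 0.541 | 52.9 |
| 8 | 0.0428 | 0.7742 | 0.694 | 46.9 |

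Moving the final cut-off does not rescue a boundary of 5. A cut-off of 21 gives type I error 0.0813; a cut-off of 23 gives type I error 0.0273 and power 0.740.

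**Expected N under the null.**

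- r1 = 7: 35 + 39 × (1 − 0.5409) = 52.9.
- r1 = 5: 35 + 39 × (1 − 0.2266) = 65.2.
- Difference: 65.2 − 52.9 = 12.3 patients.

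**How often the two rules disagree.** They differ only at 6 or 7 responses.

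- At ORR 21%: P(6) + P(7) = 0.1496 + 0.1647 = 0.314.
- At ORR 34%: 0.0147 + 0.0313 = 0.046.

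**What continuing from the disputed counts would buy.** Reaching 22 requires 16 of 39 Stage 2 responses from a start of 6, or 15 of 39 from a start of 7.

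- At ORR 21%: 0.4% from 6 and 1.0% from 7.
- At ORR 34%: 22% from 6 and 33% from 7.

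**The case against.** Several points on the other side are fair.

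- **Error control survives.** With a boundary of 5, type I error is 0.0484, still under 0.05, and power is slightly higher. A futility boundary set too low cannot produce a false claim of activity here. This stands and limits the harm to the stopping decision and patient exposure.
- **The SAP has it right.** Protocol section 8 leaves analysis detail to the SAP, which gives 7 every time. Four of the five statements agree, and a statistician working from the SAP would apply 7. This lowers the practical risk. However, the SAP does not say that it overrides the protocol, and the protocol is the document submitted to ethics committees.
- **The decision is not purely mechanical.** Protocol 8.1 says all Stage 1 data inform the transition, SAP 3.1 refers to the IDMC charter, and Protocol 8.3.4.1 allows suspension or termination for apparent futility. Even so, each rule says the cohort or substudy will be stopped at its boundary, so discretion softens the conflict without removing it.
- **The silence of SAP 6.8 proves little.** The SAP matches Protocol 8.1.1, so its authors may have seen no change to report. This is accepted; the finding rests on the protocol's own contradiction.
- **Substudy 1 is not the largest substudy.** Substudy 4 plans about 100 patients across two cohorts. Substudy 1, with 74, is the largest single cohort.

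**Conclusion.** The inconsistency is real and must be fixed. The boundary of five in Protocol 8.3.4.1 is the outlier: it conflicts with Protocol 8.1.1, with the SAP, and with the design's stated type I error and power, which only a boundary of 7 reproduces.

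If 8.3.4.1 were followed, the chance of stopping an inactive regimen at Stage 1 would fall from 54.1% to 22.7%, at a cost of about 12 extra patients on average under the null. The two rules would disagree in 31.4% of trials at a true ORR of 21%. False-positive risk remains controlled under either rule.

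The calculations assume independent binomial responses, exactly 35 and 74 evaluable patients, and no discretionary departure from the written rule. The version history says Version 5.0 followed interim results of Substudy 1. The documents do not say whether that was the formal Stage 1 analysis and give no response count, so nothing here implies that a boundary was misapplied.

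**What to change.** In the Substudy 1 bullet of Protocol 8.3.4.1, replace five with seven, so that the substudy stops at 7 or fewer and continues at 8 or more of 35. No other number in the design changes, and the SAP rule needs no edit.

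Because interim results may already have been seen, the correction should not be made silently. The sponsor should state, in the amendment and the clinical study report, which boundary was or will be applied at the Stage 1 analysis and the response count at that decision.

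The cost is one word of text plus the amendment review and ethics submission required by Protocol 9.5. It needs no new data and no extra patients.
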